# 5.3 Inclusion of Vulnerable Participants

Participants between 16 and 18 years of age may be enrolled in this study. Older adolescents have the capacity to provide adequate assent in an intensive Phase 2a study for which benefit in this disorder remains uncertain. Younger children are excluded because of the intensity of the procedures with uncertain clinical benefit.

# 5.4 Lifestyle Considerations

Not applicable.

### 5.5 Screen Failures

Screen failures are defined as participants who consent to participate in the clinical trial but are not subsequently assigned to the study intervention or entered in the study. A minimal set of screen failure information is required to ensure transparent reporting of screen failure participants, to meet the Consolidated Standards of Reporting Trials (CONSORT) publishing requirements and to respond to queries from regulatory authorities. Minimal information includes demography, screen failure details, eligibility criteria, and any serious adverse event (SAE). Due to the ultra-orphan nature of ADH1, all data derived from participants during screening will be entered into the clinical trial database regardless of whether an individual participant is included or excluded from the active treatment periods.

Individuals who do not meet the criteria for participation in this trial (screen failure) because of a failing to meet criteria outlined in Section 5 may be rescreened once. The PI will discuss with Sponsor if additional screening attempts are warranted so that a joint decision can be made and recorded if necessary for a specific participant. Rescreened participants should be assigned the same participant number as for the initial screening.

### 5.6 Strategies for Recruitment and Retention

ADH1 is a rare disease with varying estimates on the order of 1500 patient prevalence in the United States. ADH1 is designated as an orphan disease consistent with this ultra-rare prevalence. A number of participants are identified and known to NIH investigators, some of whom have participated in prior clinical evaluations at the NIH in a prior pilot study utilizing a related calcilytic compound, NPSP795 (Roberts et al 2019). Initial recruitment will include contacting known potential participants with ADH1. Additional recruitment may proceed through referrals from worldwide clinical and research experts involved in this specialized area of mineral metabolism. Finally, outreach through patient advocacy organizations worldwide will also be pursued.

While most established ADH1 patients aged  $\geq$  16 years old will likely be eligible to participate according to protocol inclusion/exclusion criterion, it is estimated that up to 20 potential participants may be enrolled to support up to 16 participants entering the treatment phase of the study.

Potential participants will undergo the informed consent/assent process and be screened during an admission to the NIH, when they will receive explanation of the clinical trial procedures and requirements. Participants will receive expert clinical oversight of their outpatient therapeutic regimen and management from NIH investigators during the period from screening to the first in-house admission and throughout the clinical trial to encourage and enhance retention.

### 5.6.1 *Costs*

Compensation (see below) for participation in the trial will be per NIH guidelines as described in the Informed Consent and related attachments. Participants will not be billed by NIH and the Sponsor for any research or related clinical care that participants will receive at the NIH Clinical Center for this study. The NIH Clinical Center will provide short-term medical care for any injury resulting from participation in this clinical trial. Costs for local medical care related to the clinical trial but not otherwise covered by participant's own insurance may be compensated by the Sponsor.

# 5.6.2 Compensation

Participants will be compensated for participation in this clinical trial via check or direct deposit to the adult or minor participant. If the minor does not have a bank account or is unable to deposit checks, an alternative arrangement will be made with the participant and parent/guardian.

Maximum compensation will be \$2550, paid in \$850 installments at the completion of the first three study periods. Participants will not be compensated for participation in the LTE.

If participant is unable to finish the study, he/she will receive adjusted compensation for part(s) completed also in accordance with NIH HRPP policy 3014-302 Subject Recruitment and Compensation.

Air/train/bus travel will be arranged by the NIH travel agency unless there are extenuating circumstances requiring the participant to book his/her own travel. For minor participants, travel and Children's Inn/hotel accommodation will also be provided for 1 parent or legal guardian. Miscellaneous out-of-pocket travel expenses (e.g., baggage receipts, airport parking, taxis) will be reimbursed if a receipt is provided. Participants traveling by car from > 50 miles will be reimbursed mileage per NIH policies. Participant copays or co-insurance for local laboratories will be paid or reimbursed if an invoice or receipt is provided.

### 6 STUDY INTERVENTION

# 6.1 Study Interventions(s) Administration

During **Period 1** participants from Cohort 1 will receive CLTX-305 (encaleret) QD and BID per protocol with water as described in Section 8.2.1.

During **Period 2** participants from both Cohort 1 and Cohort 2 will receive CLTX-305 (encaleret) BID with water as described in Section 8.2.2

During **Period 3** participants from both Cohort 1 and Cohort 2 who enter Period 3 will be discharged home to continue taking CLTX-305 (encaleret) BID with water as described in Section 8.2.3.

During LTE participants who have completed Period 3 will continue taking CLTX-305 (encaleret) BID with water as an outpatient as described in Section 8.2.4.

# 6.1.1 Study Intervention Description

The investigational medicinal product (IMP), CLTX-305 (encaleret), will be provided as white film-coated tablets containing encaleret sulfate drug substance (active ingredient encaleret) and may be provided in 5, 10, 30 and 60 mg doses in bottles. If the 5mg tablet is not available for use, then the 10 mg tablets may be split according to the related specifications indicated in the Pharmacy manual provided by the Sponsor. No other dose strength may be split.

If the 10 mg tablet needs to be split, the participant should cut one 10 mg encaleret tablet each day and take half of the tablet in the morning and the other half of the split tablet in the evening, assuring that the participant receives a full 10 mg dose per day. Participant should follow the manufacturer instructions for use included with the pill cutter. In the event that half of the split 10 mg tablet is lost, the participant should cut a new tablet in half for the evening dose and discard the remaining half. The participant should start with a new 10 mg tablet the following morning.

Full details regarding CLTX-305 (encaleret) packaging are provided in the Pharmacy Manual.

### 6.1.2 Dosing and Administration

For details on Dosing of CLTX-305 (encaleret) see Section 8.2.

For additional background on Dose Justification see Section 4.3.

Dosing of CLTX-305 (encaleret) in participants with ADH1 is informed by prior experience of both acute and chronic dosing of CLTX-305 (encaleret) in the osteoporosis program that included exposures up to 1 year primarily in postmenopausal women with presumed normal CaSR function. The proposed starting dose is 30 mg in ADH1 because this is a dose proven to result in acute elevations in cCa in euparathyroid participants without an ADH1 mutations.

Based on peer-reviewed data from a pilot human study of a related calcilytic agent, NPSP795 (Roberts et al 2019), which also studied a top dose known to cause a rise in calcium in euparathyroid participants but not in ADH1 participants, we anticipate that the starting dose of 30 mg may be ineffective or minimally effective but represents a rational initial dose that has been demonstrated as safe and well tolerated previously.

Because a comprehensive safety database exists from the prior osteoporosis development program, including 12 months or more duration of safety exposure, the current first-in-ADH1 study will include repeat dosing, dose-escalation and dose individualization over time in individual ADH1 participants. Similar to cross-over designs, conducting dose-escalation within participants should reduce variability and increase the precision of dose/response modeling compared to an approach that might use separate parallel or sequential cohorts. Up to 16 participants studied should be feasible and allow characterization of individual and group mean dose-exposure-response profiles as well as proof-of-concept on elevation of cCa. Our approach is preferable since the ultra-orphan nature of the disease makes conventional parallel group dose finding not feasible.

CLTX-305 (encaleret) will be tested both as a single daily dose and as a twice daily dose. In the prior osteoporosis program CLTX-305 (encaleret) was administered once daily and this was seen to stimulate a transient increase (spike) in iPTH levels secretion within 2 hours and a second lower plateau level of iPTH (still elevated compared to baseline) for up to 12 hours at doses of 30 mg and above. Despite both PK (drug exposure) and PD (increased iPTH levels) lasting less than 24 hours, some evidence for increased trough cCa (measured 24 hours after last dose) suggests that once daily dosing and once-daily dose escalation should be tested in ADH1 participants.

CLTX-305 (encaleret) may be administered within 30 minutes prior to meals. Administration with meals was shown in prior Phase 1 trials to be associated with adequate systemic absorption, prompt increases in plasma levels of iPTH but with a slightly blunted PTH Cmax compared to administration while fasted (See Investigator's Brochure for details and results of Phase I trials). Recommendation for administration within 30 minutes prior to meals was chosen as the paradigm for ADH1 dosing because, unlike in the osteoporosis program, the goal in ADH1 patients is not to maximize PTH Cmax but to facilitate increased iPTH levels above baseline throughout the day, adequate to raise blood cCa levels into the normal range. It is anticipated, however, that twice daily dosing may result in lower iPTH levels Cmax and more stable iPTH level over the course of 24 hours versus single daily dosing. The protocol is designed to test this hypothesis by conducting both once-daily and twice daily dose escalation in Period 1 and twice-daily dose escalations in Period 2.

An overview and general description of the study strategy for intervention CLTX-305 (encaleret) administration is presented below. Additional detail on doses, regimens and titration algorithm/guidance for each Period can be found under the appropriate sub-section of Section 8.2, including flowcharts for dosing in Period 1 (Figure E) and Period 2 (Figure F).

# 6.1.3 Period 1 (Single Ascending Dose Escalation and BID PK/PD profile) – Cohort 1

In Period 1, eligible Cohort 1 participants are admitted to the NIH CC after completing screening tests. On days 1-3 of admission, Cohort 1 participants will undergo single daily dosing and protocol-specified dose-escalation of CLTX-305 (encaleret) from the initial dose of 30 mg on Day 1, increasing to a maximum dose of 180 mg on Day 3. Based on the individualized responses to QD dose escalation an individualized dose of CLTX-305 (encaleret) will be chosen for BID administration on Days 4 and 5.

Days 1, 2 and 3 (QD Dose Escalations): Up to 8 participants (minimum of 5) will undergo a single-dose, dose-escalation over the first 3 days of admission in Period 1. Morning doses will be administered on Days 1, 2 and 3, respectively, accompanied by frequent blood and urine sampling for 24-hours for PK/PD measures. CLTX-305 (encaleret) will be administered in the morning within 30 minutes prior to breakfast. If dose escalation is limited due to tolerability or hypercalcemia, then the investigator, in consultation with the Sponsor, may choose to interrupt the pre-specified dose escalation (for example see Section 6.1.7 and Section 8.2.1). In this case, the investigator, in consultation with sponsor, may choose to repeat the last well-tolerated dose on Days 2 and 3, or titrate down as appropriate.

Dose-escalation will take place sequentially on Days 1, 2 and 3 without interim wash-out because prior extensive PK-PD data supports minimal drug accumulation over 24 hours when dosed once daily (for details see the Investigator's Brochure). Similarly, it is expected that iPTH levels will not remain elevated for 24 hours after dosing when CLTX-305 (encaleret) is administered once-daily. However, any carryover effects that may occur should not confound the objective of demonstrating an acutely efficacious dose of CLTX-305 (encaleret). For any given participant, cCa values > 10.5 mg/dL, during a dosing interval, will indicate that a top dose of CLTX-305 (encaleret) has been reached for that individual and further dose escalation will not be necessary. In this scenario, the investigator, in consultation with the Sponsor, may choose to repeat the last well-tolerated dose on the remaining QD testing days (e.g., Days 2 and 3), as appropriate. Detailed examples of dose and titration modifications based on the cCa response are shown in Figure E in Section 8.2.

# 6.1.5 Period 3 (Cohort 1 and Cohort 2) – Outpatient Dosing

In Period 3, the initial outpatient dose of CLTX-305 (encaleret) will be individualized based on the results from inpatient Periods 1 and/or 2 as described in greater detail in Section 8.2.3. Period 3 will include a titration phase of approximately 12 weeks and a maintenance phase of approximately 12 weeks for a total outpatient exposure to CLTX-305 (encaleret) of 24 weeks. Titration will be conducted by the NIH investigators at scheduled or unscheduled telephone contact visits based on review of outpatient chemistry results for cCa, Mg, phosphorous at NIH CC visits (approximately every 8 weeks) based on assessment of both blood and urine calcium results as described, with the goal of optimizing the CLTX-305 (encaleret) dose without calcitriol, targeting normal cCa and phosphorus concentrations, avoiding symptoms of hypo- or hypercalcemia, and minimizing the extent of hypercalciuria. Oral calcium supplementation may be used as needed on top of a minimum daily dietary intake of at least 1000 mg.

# 6.1.6 Long-term Extension (Cohort 1 and Cohort 2) – Outpatient Dosing

In the Long-term Extension (LTE), participants will continue CLTX-305 (encaleret) per the dosing regimen established in the maintenance phase of Period 3. Telephone contacts along with outpatient laboratory assessments will be performed every 6 months starting at Month 3 with NIH CC visits occurring every 6 months starting at Month 6. CLTX-305 (encaleret) doses may be titrated as needed based on assessment of both blood and urine results as described, with the goal of optimizing the CLTX-305 (encaleret) dose without calcitriol, targeting normal cCa and phosphorus concentrations, avoiding symptoms of hypo- or hypercalcemia, and minimizing the extent of hypercalciuria. Oral calcium supplementation may be used as needed on top of a minimum daily dietary intake of at least 1000 mg.

### 6.1.7 Dose Limiting Toxicity

The goal of the current study in participants with ADH1, is to elevate cCa concentrations, including identifying doses capable of raising cCa beyond the normal range. It is important to establish if an allosteric modulator of the CaSR is capable of causing hypercalcemia at all, in patients with activating mutations of the CaSR. The study is designed to monitor for cCa elevations in a closely supervised and expert setting familiar with acute treatment and intervention, if necessary. In the prior osteoporosis program, hypercalcemia, identified by laboratory testing, was confirmed as a dose-limiting effect in presumed euthyroid participants without *CaSR* mutations, however, of note, laboratory hypercalcemia was not clearly associated with hypercalcemic symptoms; the events were detected in routine laboratory

monitoring and were managed by withholding or lowering the dose of CLTX-305 (encaleret).

Another inherent study objective is assessment of safety and tolerability across different doses and regimens including characterizing dose-limiting adverse events, determining maximum doses associated with acceptable safety risk, as well as determining doses that can effectively raise or maintain stable normal cCa concentrations.

Based on experience accumulated in human clinical testing, from the prior osteoporosis program, no specific safety signal or adverse event profile was identified with acute or chronic dosing with CLTX-305 (encaleret). Dose-limiting hypercalcemia was the only signal that required chronic doses to be limited to 15 mg QD in an otherwise healthy population of postmenopausal women treated for up to 12 months.

Since there is no specifically expected adverse event profile or anticipated dose-limiting toxicity in humans, safety monitoring for CLTX-305 (encaleret) will be based on established approaches and principles. Protocol-specified safety measures based on adverse event monitoring, safety laboratories, vital signs, physical exam, and EKGs will be assessed during the NIH visits. For any individual participant, the experience of an adverse event will be evaluated and recorded according to the guidance given in Section 8.5.3, and appropriate action with respect to study drug administration will be made according to the judgment and assessment of the investigator.

It is expected that higher doses of CLTX-305 (encaleret) will be necessary to see comparable changes in cCa in participants with ADH1 compared to previously tested participants with normal CaSR function and therefore the current protocol stipulates potential dose escalation higher than 100 mg including doses possibly > 400 mg acutely in order to identify effective doses in the new target population of participants with abnormal CaSR function where cCa elevations would represent efficacy and not a safety side-effect.

The proposed starting dose for participants with ADH1 is 30 mg, which was well tolerated, in healthy normal volunteers, without a specific safety signal, but was also rapidly effective in raising cCa. It is expected that this dose will not be effective or may be minimally effective in raising cCa in ADH1 participants. Therefore, based on known safety and efficacy on cCa, CLTX-305 (encaleret) 30 mg represents a rational initial dose for this first-in-ADH1 trial. Moreover, CLTX-305 (encaleret) was acutely safe and well tolerated across a range from 5-100 mg in non-ADH1 participants (approximately 10-fold range). Original Phase 1, single-escalating dose trials in healthy humans with presumed normal CaSR function, were designed to escalate up to 400 mg CLTX-305 (encaleret); however, a top dose of 100 mg was identified based on rising cCa concentrations. The top dose in people with presumed normal CaSR function was chosen as 100 mg, to avoid excessive cCa elevations, and was used safely as the top dose in a Phase I thorough QTc study.

Of note, although people with ADH1 may show a right-shifted dose-response compared to healthy non-ADH1 people, there is no biological reason to expect the dose-response trajectory to be significantly steeper in participants with ADH1. Therefore, it is important to plan for appropriate dose-escalation in this first-in-ADH1 trial, to focus on proof-of-calcium-

raising effect. The planned dose range for QD exploration in ADH1 participants includes a range from 30 to 180 mg (approximately 6-fold range). If higher doses are required to confirm efficacy on cCa, dose escalation will continue but switch to BID regimens as specified in greater detail in the algorithm/guidance in Section 8.2.

In the prior osteoporosis program, hypercalcemia adverse events were not symptomatic and were identified based on scheduled periodic laboratory assessments. Dose-limiting thresholds for post- CLTX-305 (encaleret) cCa levels are specified as part of the dosing and titration algorithms in Section 8.2. In Summary, participants who achieve a post-dose cCa > 10-10.5 mg/dL (in Period 1) and cCa > 10 mg/dL (in Period 2) during the dose escalation will not proceed to higher CLTX-305 (encaleret) doses. Participants with cCa values between 10-10.5 mg/dL during dose escalation in Period 1, will have their doses increased by 30 mg only. Participants who achieve cCa > 10-10.5 mg/dL in Period 1 and >10 mg/dL in Period 2 will have their dose maintained or reduced and undergo final frequent sampling as appropriate.

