### 4 STUDY DESIGN

# 4.1 Overall Design

This will be a single-site, open-label, dose-ranging and dose maintenance study to evaluate the safety, tolerability and efficacy of CLTX-305 (encaleret) to maintain normal albumin-corrected blood calcium (cCa) in participants with hypocalcemia due to ADH1. It will consist of two inpatient periods of dose initiation, escalation and steady-state adjustment (Periods 1 and 2), an outpatient dose stabilization and maintenance period including NIH clinical visits (Period 3), and a long-term extension (LTE).

The LTE is designed to obtain additional safety data and evaluate durability of efficacy for CLTX-305 (encaleret). The LTE also allows for continued treatment of enrolled participants with CLTX-305 (encaleret). Participants who elect to continue in LTE will receive CLTX-305 (encaleret) for an additional period of time, up to 25 months (approximately 2 years) or until they transition to the CLTX-305-302/CALIBRATE Phase 3 LTE, whichever occurs first.

Two principal cohorts are planned:

- Cohort 1: up to 8 participants (minimum of 5) will initially be enrolled into Period 1 (inpatient), after which they may return to participate in Period 2 (inpatient, after at least an 8-week interval). Participants who complete Period 2 will be eligible to enter Period 3 (outpatient) for up to 24 weeks of dosing with CLTX-305 (encaleret).
- Cohort 2: up to 10 additional participants (minimum of 5) will enroll directly into Period 2 (inpatient). The initiation of Cohort 2 will be based on evaluation of accumulated data from Cohort 1. Cohort 2 participants who complete Period 2 will be eligible to enter Period 3 (outpatient) to receive up to 24 weeks of CLTX-305 (encaleret).

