# 6.1.8 Dose Modifications

See above for general principles of dosing and titration limitations based on toxicity or hypercalcemia. See Section 8.2 for details of the dosing guidance algorithm for each Period.

Dose modifications should be made according to the protocol-specified guidance/algorithm described in Section 8.2 based on cCa thresholds of > 10-10.5 mg/dL in Period 1 and > 10 mg/dL in Period 2. Similarly, titration in outpatient Period 3 and the LTE will be based primarily on periodic assessment of cCa and where cCa > 10 mg/dL would also require dose modification.

For participants who develop clinical laboratory abnormalities unrelated to the dosing algorithm parameters (e.g., corrected calcium) indicating that further conduct of per protocol clinical assessments/procedures may put the participant at risk may have their CLTX-305 (encaleret) dosing interrupted at the discretion of the principal investigator and should be captured as adverse events. Because of the intensive sampling required during the conduct of the in-hospital assessments, procedures related to the collection of blood in terms of sampling technique or frequency of sampling and/or blood volume may have their scheduled dosing interrupted so as to allow the patient to recover and continue the study treatment at a later date (re-initiation). The time interval separating the day of the interrupted dose and the day to re-initiate dosing will be less than or equal to 56 days. The participant with an interrupted dose may be re-initiated at the next protocol-specified dose level of CLTX-305 (encaleret) at the discretion of the principal investigator. A participant with a dose interruption shall continue to meet eligibility criteria for the study.

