Figure E **Dosing Guidance Algorithm for Period 1** 30 mg Day 1 If cCa max is If dose is tolerated & cCa If dose is tolerated & >10.5 mg/dL max is 10.0-10.5 mg/dL cCa max <10.0 mg/dL 60 mg 90 mg Day 2 10 mg Is dose tolerated & Is dose tolerated & cCa max If cCa max is If dose is tolerated & cCa If dose is tolerated & cCa max <10.5 mg/dL? between 10.0-10.5 mg/dL? >10.5 mg/dL max is 10.0-10.5 mg/dL cCa max <10.0 mg/dL No Yes Nο Yes Day 3 20 mg 90 mg 120 mg 180 mg 40 mg ET 60 mg Guidance for BID Dosing: To determine Day 4 & 5 BID dose, consider what QD dose meets the following criteria: cCa Criteria iPTH Criteria Day 4 & 5 . The lowest dose that resulted in an increase in cCa by ≥1 mg/dL during the dosing Peak iPTH of 150-300 pg/mL interval AND/OR OR Durable elevations in iPTH levels ≥50 pg/mL (ideally for up to 12 . The lowest dose that maintained cCa in the normal range without exceeding the upper limit of the reference range over the dosing interval If no single QD dose meets the above criteria for a given subject, then the investigator should choose the highest QD dose that was well tolerated and begin administration of that dose given once in the morning and once in the evening (BID) within 30 minutes of meals starting on the morning of Day 4. 10 - 180 mg BID

Day 6 (Discharge): After the PK/PD blood sampling is collected on the morning of Day 6 all participants will resume their prior conventional treatment regimen. During Day 6, cCa levels will be monitored throughout the day. This period can be extended if additional monitoring or treatment (e.g., to stabilize calcium) is needed prior to discharge.

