The first 7 participants who have completed CLTX-305-201 Period 2 and entered into Period 3 have had a wide range of CLTX-305 (encaleret) dose requirements from 10 mg once daily to 180 mg BID suggesting that CLTX-305 (encaleret) dosing is highly individualized. As a result, all remaining participants in Period 2 will receive an initial CLTX-305 (encaleret) 90 mg BID dose for at least 3-4 doses for evaluation of safety, tolerability and the ability to modulate cCa levels. The CLTX-305 (encaleret) dose will be up- or down-titrated as needed to maintain cCa levels below 10 mg/dL and blood phosphorus levels above the lower limit of normal. Dosing will be adjusted in 5, 10, 30, or 60 mg increments based on the available CLTX-305 (encaleret) tablet strengths. A frequent sampling test day with additional serial blood and urine sampling to assess 24-hour PK/PD profiles will be performed on Day 5. For details on the PK/PD timepoints during frequent sampling on Day 5 see Section 1.3.1 specifically Table J and Table K.

The total blood volume collected during Period 2 for Cohort 1 participants will be less than the blood volume limits per participant as per NIH Guidelines for Blood Draw Limits for Research Purposes (M95-9, June 2009). These volumes include the cumulative potential collection over an 8-week period: -10-14-day labs, Day -1 safety labs, Period 2 inpatient week, and 4 weeks of outpatient labs in Period 3. If a participant has a low body weight (<43 kg for adults or <48 kg for adolescents), the blood volume taken will be reduced to remain within the NIH guidelines of 10.5mL/kg/8w (adult) and 9.5 mL/kg/8w (pediatric). If, at any time, the CLTX-305 (encaleret) dose is associated with a cCa > 10 mg/dL, then the dose should be reduced to a lower dose level. An example of how CLTX-305 (encaleret) dosing may be adjusted is provided in Figure F below.

Figure F Dosing Guidance Algorithm for Period 2 – Cohort 1

BID= Two doses/day

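### Does a calcium cut-off written as a range in Protocol 6.1.7, with different Period 2 wording in 8.2.2, call for a change to the plan?

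*Protocol*

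**What the plan says.** Protocol 6.1.7 closes with a summary paragraph on albumin-corrected calcium (cCa). It contains three statements that matter here.

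- No higher dose for "participants who achieve a post-dose cCa > 10-10.5 mg/dL (in Period 1"), nor for those above 10 mg/dL in Period 2.
- For results inside the Period 1 range, the paragraph goes on: "Participants with cCa values between 10-10.5 mg/dL during dose escalation in Period 1, will have their doses increased by 30 mg only".
- For results beyond the limit in either period, it then adds: "Participants who achieve cCa > 10-10.5 mg/dL in Period 1 and >10 mg/dL in Period 2 will have their dose maintained or reduced".

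Section 6.1.8 repeats the notation and says dose modifications are "based on cCa thresholds of > 10-10.5 mg/dL in Period 1 and > 10 mg/dL in Period 2". Both sections send the reader to Section 8.2 for the working algorithm.

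Elsewhere the Period 1 limit is a single number. Section 6.1.3 says that "cCa values > 10.5 mg/dL, during a dosing interval, will indicate that a top dose of CLTX-305 (encaleret) has been reached". Figure E in 8.2.1, whose box text runs together when extracted, sorts the Day 1 result into ">10.5 mg/dL max is 10.0-10.5 mg/dL cCa max <10.0 mg/dL".

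For Cohort 1 in Period 2, Section 8.2.2 says: "If, at any time, the CLTX-305 (encaleret) dose is associated with a cCa > 10 mg/dL, then the dose should be reduced". The Cohort 2 text in the same section sets a titration target of below 10 mg/dL and has no matching sentence.

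On numbers, Section 4.1 states that "up to 8 participants (minimum of 5) will initially be enrolled into Period 1".

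**The concern.** A greater-than sign followed by a range does not fix a cut-off. If the range is read from its lower end, one paragraph of 6.1.7 gives incompatible instructions for the same calcium value: do not escalate, escalate by 30 mg, and hold or lower the dose. In Period 2 the threshold is the same in 6.1.7 and 8.2.2, but the permitted actions differ, because holding the dose is allowed in one and not in the other.

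Hypercalcemia is the expected on-target, dose-limiting effect of this drug, so these are the protocol's main written safety rules for dosing. Ambiguity could mean that similar participants were handled differently. It could also leave it unclear which dosing decisions count as protocol deviations, which SAP 13.2 tabulates by Period when they are judged important.

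**Working it through.** There is no sample-size or power figure to reproduce; Protocol 9.1 plans description only. The check sets the passages side by side and applies each to one value, cCa = 10.2 mg/dL.

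**Period 1**

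| Source | Range read as above 10.0 | Range read as above 10.5 |
|---|---|---|
| 6.1.7, first statement | no higher dose | does not apply |
| 6.1.7, second statement | 30 mg increase | 30 mg increase |
| 6.1.7, third statement | hold or lower | does not apply |
| 6.1.3 | not a top dose | not a top dose |
| Figure E | middle band | middle band |

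The Figure E middle band takes 30 mg on Day 1 to 60 mg on Day 2. The step is 60 − 30 = 30 mg, the same as the second statement of 6.1.7. The three Day 1 bands (below 10.0, 10.0 to 10.5, above 10.5) cover every value once with no overlap.

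Reading the range from 10.0 contradicts the rest of its own paragraph, 6.1.3 and Figure E. Reading it from 10.5 leaves no contradiction. This shows which reading makes the text coherent. It is not a view on which cut-off is clinically right.

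**Period 2, Cohort 1**

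| Action at 10.2 mg/dL | Fits 6.1.7? | Fits 8.2.2? |
|---|---|---|
| Lower the dose | yes | yes |
| Hold the dose | yes | no |

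Choosing a number does not remove this difference, since both sections use 10 mg/dL. Part of it may come from the third statement of 6.1.7 covering both periods in one sentence. Holding a dose has a clear place in Period 1, where 6.1.3 allows the last well-tolerated dose to be repeated.

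**Who and what could be affected**

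- Only Cohort 1 enters Period 1, and the 8.2.2 sentence is in the Cohort 1 text. Each issue therefore concerns at most 8 participants. The documents do not say how many had values in question.
- SAP 13.7.1 records that no intercurrent-event strategy was set before all subjects had completed Period 3 Week 24, and that none stopped early. Dosing in Periods 1 and 2 has therefore finished.
- SAP 11.1 runs all safety and efficacy analyses on everyone who took at least one dose in the period. SAP 11.2 defines the PK set by dosing and having a concentration result. There is no per-protocol set, so classifying a dosing decision as a deviation removes nobody.
- SAP 13.3.1 summarizes exposure for Period 3 and the LTE only.

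Only a count in the important-deviations summary could move.

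**The case for a change.** The strongest argument for acting rests on Period 2. Section 6.1.7 points to Section 8.2 for thresholds but then states actions of its own, and those actions do not match 8.2.2. Protocol 10.9.1 defines a deviation as any departure from the approved protocol. Protocol 10.5 says the algorithm guides dosing decisions. The readable text does not say whether departing from guidance is a deviation, or which section is the reference. A Cohort 1 participant kept on dose above 10 mg/dL could be classified either way, and that question outlives the dosing itself.

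The difference in permitted action stands, as does the loose Period 1 notation. The step to a plan change does not. Protocol 10.9 and SAP 13.2 place the detail of identifying and managing deviations in a separate data monitoring plan, and SAP 13.2 has the sponsor and study team review and categorize the important ones. Silence in the protocol and SAP does not show that the matter is unaddressed. A protocol amendment would need IRB review under the Statement of Compliance, and it would edit rules for periods that have ended.

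Two related points add little. Section 4.1 and SAP 8.0 mention an upper limit of normal without a number, but Figure F could not be read in the copy reviewed and may supply it. Some passages still base the Cohort 1 starting dose in Period 2 on Period 1 responses, but 8.2.2 itself limits the fixed start to the participants remaining after the first 7.

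**Conclusion.** This is a clerical inconsistency in a summary paragraph, with no gain from changing the plan. The Period 1 wording is resolved by the section to which it refers. The Period 2 wording leaves one uncertain case, a held dose above 10 mg/dL in Cohort 1, among at most 8 participants. No endpoint, analysis set, paired test or conclusion depends on it, and no participant can be protected by editing it now.

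Sections 6.1.7 and 6.1.8 do disagree in wording with 6.1.3, Figure E and 8.2.2. Reconciling them, and choosing which rule stands, belongs to the sponsor and investigators. If a held dose of this kind comes up in the deviation review, a sentence in the clinical study report naming the passage used as reference would be enough.

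This rests on three assumptions: that SAP 13.7.1 means what it says about all subjects having completed Week 24; that the Figure E bands are read correctly from its extracted text; and that neither Figure F nor SAP 10.13, which could not be seen, contradicts the passages used here.
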